## **Statistical Analysis Plan**

**Specific Aim 1:** Repeated measures analysis of variance (ANOVA) will be used to assess differences between intervention and control groups on outcomes variables over time. Post-hoc analysis will be based on Fisher's least significant difference procedure for pairwise comparisons. Baseline comparisons between those who dropped out and those who completed all three waves of data collection will be determined using two-sample t-tests or chi-square tests, and the rate of retention will be compared between the two treatment arms using the chi-square test of association to assess whether differential drop-out occurred.

**Specific Aim 2:** Kaplan-Myer survival analysis with a logrank test will be used to make an overall comparison between time to rehospitalization or death event between intervention and control groups. Cox proportional hazards model will be used to estimate the hazard ratio of intervention effect on the prediction of the end-point of rehospitalization or death compared to usual care group, while controlling potential compounding factors.

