After eligible patient-caregiver dyads sign the consent forms, they will participant in this study. Baseline data will be collected during a home visit. At the baseline assessment, they will fill out questionnaires using the RedCap system and collect 24-hour urine specimens. Urine containers, collection devices (urinals for men and toilet "hats" for women) and written instructions will be provided. The research assistant will interview participants to obtain demographic characteristics and to confirm their comorbidities. Information about demographics and comorbidities will be obtained using a structured questionnaire in interview. A research assistant and the dyads will set up the starting day of urine collection within 3 days of completion of questionnaires and pick up dyad's urine specimens in the dyad's home and deliver University of Kentucky Chandler Hospital Laboratory to determine 24-hour urinary sodium excretion level. Additional data collection for qualitative data, and diet quality will be also collected by home visiting. The medical chart will be reviewed to confirm only patients' comorbidities. After patients are categorized as adherent or non- adherent using 3000mg urine sodium cut point, the dyads will be randomly assigned to the Family SWaP intervention or usual care group using stratified randomization. Caregivers' adherence level at baseline will not be used in randomization but will be used to compare adherence at follow up. Dyads in the Family SWaP intervention will participate in a 16-week intervention delivered by the interventionist. The usual care patients will receive the standard medical and nursing care for HF patients provided at the clinics from which they were recruited. The usual care dyads will participate in the same data collection procedures as dyads in the intervention group. Follow-up data collection will be conducted 4 and 12 months after the intervention group completes the 16 week intervention to evaluate short and long term effects. At each follow-up, patient-caregiver dyads will complete the same questionnaires as baseline. Self-report of all hospitalization events will be collected from patients/family caregiver via monthly phone calls and a hospitalization logbook kept by the dyad for 12months. The medical record and administrative database will be queried to confirm rehospitalizations by the research nurse who will be blinded to the study group assignment. Data from the optional recorded interviews will be transcribed by a HIPAA compliant third party transcription service (REV).

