There is no monetary incentive to compensate for their time during 12 months. However, each dyad (patients and their family caregiver dyad) who participant in this study will receive an iPad per family at the beginning of the study. If any one of the dyad members withdraws the study before three assessments complete, we consider patient-caregiver dyad as a unit of the study will end the study and they should return the iPad that will be given during the study. When two dyad members complete all three assessments during 12 months study, the dyad will keep the iPad. Free data plan will be provided for only dyads that don't have home Wi-Fi access during the study (12 months).

**Costs to Subjects:** Describe any costs for care associated with research (including a breakdown of standard of care procedures versus research procedures), costs of test drugs or devices, and research procedure costs that are the subject's responsibility as a consequence of participating in the research. Describe any offer for reimbursement of costs by the sponsor for research related injury care.

There will be no additional costs to the participants and no personal travel costs to the research site.

**Data and Safety Monitoring:** The IRB requires review and approval of data and safety monitoring plans for greater than minimal risk research, clinical research, or NIH-funded/FDA-regulated clinical investigations.

If you are conducting greater than minimal risk research, clinical research, or your clinical investigation is NIH-funded/FDA-regulated, describe your Data and Safety Monitoring Plan (DSMP). [Click here for additional guidance on developing a Data and Safety Monitoring Plan.](#)

If this is a *non-sponsored investigator-initiated* protocol considered greater than minimal risk research, clinical research, or your clinical investigation is FDA-regulated, *and* if you are planning on using a Data and Safety Monitoring Board (DSMB) as part of your

DSMP, [click here for additional guidance](#) for information to include with your IRB application.

If relying on an independent agent or committee for DSMB services, it is the PI's responsibility to establish the services with the agent or committee. Please be reminded that the PI must submit DSMB reports to the IRB via modification or continuing review. 

We have developed a detailed Data Safety Monitoring Plan that includes the following elements.

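### One member's withdrawal ends follow-up for the whole dyad, and Aim 1's repeated measures ANOVA has no stated missing-data method

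*Combined protocol and SAP*

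**What the plan says.** The withdrawal rule is in the protocol's Research Description, under Payment. If either member withdraws too early, the pair stops together: "three assessments complete, we consider patient-caregiver dyad as a unit of the study will end the study". Returning the iPad follows as a second consequence. The same paragraph lets the pair keep it on full completion: "When two dyad members complete all three assessments during 12 months study, the dyad will keep the iPad".

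Study Design names outcomes for patients and caregivers, and Research Procedures has both members repeat the baseline questionnaires at each follow-up. Neither section says what happens to a member whose partner has left.

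For Aim 1 the SAP states: "Repeated measures analysis of variance (ANOVA) will be used to assess differences between intervention and control groups on outcomes variables over time". Post-hoc tests follow Fisher's "least significant difference procedure for pairwise comparisons". Dropout is addressed in two ways. Baseline values are compared between "those who dropped out and those who completed all three waves of data collection", and "the rate of retention will be compared between the two treatment arms using the chi-square test of association". The text gives no estimation method, analysis population or missing-data rule.

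**The concern.** Two losses can build on each other. First, the dyad rule stops measurement of someone who may be willing to go on, so obtainable data are given up. Second, classical repeated measures ANOVA needs every wave. Anyone with baseline and first follow-up but no last follow-up would then leave the analysis altogether, including values already collected.

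The SAP's two dropout checks describe loss and do not correct for it. Equal retention in the two arms does not show that the same kinds of people left. At stake are precision in both roles and, if departure depends on response differently by arm, the size of the estimated effect.

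**Working it through.** **Inputs.** The protocol gives 300 dyads (600 people) and three waves. It gives no withdrawal rate, effect size or correlation in the text available, so there is no plan figure to reproduce. Everything below that line is assumed: 1:1 allocation, two-sided 5% test, 80% power, unit SD.

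**Does the classical method drop observed values?** A standard repeated measures ANOVA routine was given 20 subjects and three waves, with 4 subjects missing the last. It rejected the data as unbalanced. Reducing to complete cases kept 48 of 56 observed values and discarded 8 (4 baseline, 4 first follow-up).

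**Precision cost of the dyad rule.** Let p be each member's withdrawal probability and φ the within-dyad correlation of withdrawal.

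- Dyads retained = (1−p)² + φp(1−p)
- Willing members cut off = 600 × p(1−p)(1−φ)
- Detectable difference at full size = 2.80 × √(2/150) = 0.323 SD. Divide by √(retained) under the dyad rule, or by √(1−p) if only the withdrawing member is lost.

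| φ | p | Dyad loss | Willing members cut off | Detectable, dyad rule | Detectable, own withdrawal only | Ratio |
|---|---|---|---|---|---|---|
| 0.5 | 10% | 14.5% | 27 | 0.350 | 0.341 | 1.026 |
| 0.5 | 15% | 21.4% | 38 | 0.365 | 0.351 | 1.040 |
| 0.5 | 20% | 28.0% | 48 | 0.381 | 0.362 | 1.054 |
| 0 | 10% | 19.0% | 54 | 0.359 | 0.341 | 1.054 |
| 0 | 15% | 27.8% | 77 | 0.381 | 0.351 | 1.085 |
| 0 | 20% | 36.0% | 96 | 0.404 | 0.362 | 1.118 |

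At φ = 1 the retained fraction is 1−p and the rule costs nothing extra.

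**Bias of a completer analysis.** This was simulated with higher values better and a true effect of 0.30 SD at both follow-ups. Assumed correlations were 0.40 (baseline with first follow-up), 0.60 (first with last) and 0.35 (baseline with last). Dropout after the first follow-up is 20% in each arm. In the intervention arm only, it depends on the observed first follow-up value through a logistic slope per SD.

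| Who leaves | Slope | Completers, last follow-up | Completers, change from baseline | All-data likelihood |
|---|---|---|---|---|
| Poor responders | −0.5 | 0.358 | 0.320 | 0.30 |
| Poor responders | −1.0 | 0.403 | 0.334 | 0.30 |
| Good responders | +0.5 | 0.242 | 0.283 | 0.30 |
| Good responders | +1.0 | 0.198 | 0.268 | 0.30 |

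When poor responders leave, completers also show 0.40 or 0.47 at the first follow-up, although every value at that wave was collected. For scale, with 120 per arm the standard error is √(2/120) = 0.129 at one wave. For change it is √(2 × 1.3/120) = 0.147, where 1.3 = 2(1 − 0.35).

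**Does the dyad rule itself bias the patient comparison?** Here the patient's own withdrawal is random, and caregiver-only exit of 4.5-16% is tied to the patient's first follow-up value in the intervention arm. Completers show 0.31-0.40 at the last follow-up if caregivers of poor responders leave and 0.20-0.29 if caregivers of good responders leave. On change the range is 0.27-0.34. With the dyad rule left in place, the likelihood analysis still returns about 0.30. In this scenario the bias therefore comes from the completer analysis.

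**Limits.** If dropout depends on the unseen last value (slope −0.5 or −1.0), completers show 0.395 or 0.471 and the likelihood analysis 0.360 or 0.41. The share of bias removed is (0.095 − 0.060)/0.095 = 37%, or (0.171 − 0.11)/0.171 = 36%. With equal slopes and equal rates in both arms, completers return 0.30. With one identical dropout model in both arms (slope −0.5 or −1.0, 20% dropout in controls), the true effect makes the rates differ (20% against 18% or 16%), and completers show 0.294 or 0.283.

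**The case against.** The strongest reply has four parts.

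- The SAP never says incomplete cases are excluded. A reader might infer that it commits to discarding first follow-up values, but that rests on the conventional form of the method. A mixed-model implementation would keep them. This stands: the defensible statement is that handling is unstated and the named method, taken classically, would drop them.
- A reader might infer that the dyad rule biases the patient comparison. The check does not support this where caregiver exit depends on observed values, because a likelihood analysis recovers the effect with the rule in place. The rule adds bias beyond that only if exit depends on patient outcomes that were not observed.
- Nearly doubled loss is the independent case. Caregivers must live with the patient, and one iPad is shared and kept only if both finish. Joint departure is therefore likely, and the lower range is the more plausible.
- Bias on change from baseline, which is close to the group-by-time question, is at most about a quarter of a standard error in these examples. The last follow-up figures are larger and still matter, because pairwise comparisons are planned.

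A reader might also infer that Aim 2 events are lost when a dyad ends. The documents do not support that. Some reporting depends on the dyad ("via monthly phone calls and a hospitalization logbook kept by the dyad for 12months"), but a record query and a hospital-completed event form are also planned.

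That the dyad is the unit of randomization explains joint allocation. It does not require measurement of a consenting person to stop.

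**Conclusion.** The point holds as a cheap improvement. The rule gives up obtainable follow-up, and Aim 1 lacks a missing-data method. For member withdrawal of 10-20%, the rule's demonstrated cost is a detectable difference 3-5% larger at correlation 0.5, or 5-12% larger under independence. It is nil if members always leave together.

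A completer analysis could move a true 0.30 SD to anywhere in 0.20-0.40 at the last follow-up, or about 0.27-0.34 on change, if dropout tracks response in one arm only. It is unbiased if dropout is unrelated to outcome, or has equal slopes and equal rates in both arms. An identical dropout model combined with a real effect leaves a small bias.

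All rates, slopes and correlations are assumptions. A likelihood analysis relies on missing at random and removes only about a third of the bias when dropout depends on unseen values.

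**What to change.** 1. **Protocol, Payment.** State that a member's withdrawal ends only that member's data collection, and that the remaining member, if willing, is asked to complete the remaining assessments. The iPad return rule can stay as a separate matter. Whether the programme continues for that member is for the investigator.
2. **SAP, Specific Aim 1.** Replace repeated measures ANOVA with a likelihood-based mixed model for repeated measures (arm by categorical time). Use all available observations from all randomized participants, analysed as randomized, with a dyad effect if both members are modelled together. State the missing-at-random assumption and how values after death are treated, since Aim 2 anticipates deaths. Keep the retention chi-square as description.

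The cost is protocol, consent and SAP wording. The downsides are some one-member dyads and reliance on missing at random.

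One matter should be raised separately. Research Procedures places the assessments after the programme ends ("Follow-up data collection will be conducted 4 and 12 months after the intervention group completes the 16 week intervention"), while Payment describes three assessments within a 12-month study. These sections must be reconciled.
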